9.2.1.1. Collection of Specimens

No changes will be made to the routine clinical care of patients in this study. All aspects of the surgical management including preoperative and postoperative care will be carried out per the standard of care. Specimens will be collected for the study during tumor resection. The study

will not affect the manner or quantity of tissue removed. In addition to the bulk tumor specimen as routinely sent, numerous small specimens will be collected during the resection using tumor forceps at sampling positions registered to pre-operative MRI images using a navigation system (General Electric Instatrak or BrainLab Vector Vision). All specimens will be sent to the BWH Tissue Biorepository. When the Tissue Biorepository has confirmed that enough tissue has been collected to make a diagnosis, specimens will be made available MALDI MSI.

9.2.1.2. Handling of Specimens

Specimens for correlative analysis will be banked by the SPORE Pathology Core (Directors: [name] MD, [name]). A dedicated pathology banking assistant will track and collect tissue for fresh, frozen, and culture analysis. The tissue will be quality control screened by a banking Neuropathologist Staff and scored for percentage tumor composition, necrosis, inflammation, and normal brain tissue content. Specimens will be analyzed by MALDI MSI (Bruker Daltonics), and associated with histopathology for tumor cell prevalence and select histological features. Microscopy images of standard histopathology staining will be co-registered with mass spectrometry images of a given tissue section to resolve the molecular signature of distinct histology features such as cell density, necrosis, and vascularization. The histopathological validation will be correlated to radiology and clinical information via Mirax Digital Slide Desktop (MDSD) database (Zeiss). As part of this study, we will study the differences in the molecules that occur within different regions of the tumor (e.g. at the boundaries between tumor and normal tissues). Metabolic profiling will involve analysis of tissue pH, lactate, pyruvate, and lipid composition. Neurotransmitter profiling will involve analysis of glutamate, glutamine, and GABA composition. Drug distribution will be performed for perampanel and levetiracetam.

9.2.1.3. Shipping of Specimens

Specimens will not be shipped off site.

9.2.1.4. Sites Performing Correlative Study

Tissue analysis will be performed at BWH by [name]. All correlative analyses will be performed at BWH.

10. STUDY CALENDAR

Baseline evaluations are to be conducted within 2 weeks prior to start of protocol therapy. Scans must be done ≤ 2 weeks prior to the start of therapy. If the participant's condition is deteriorating, laboratory evaluations should be repeated within 48 hours of assessment. Study visits will be performed at monthly intervals by clinic or phone interviews. Clinical response will be evaluated at each study visit. Adverse events will be assessed with each study visit at minimum, and more frequently as clinically indicated.

	Baseline	Pre-surgery	During surgery	Post-surgery maintenance	Off Study ^d
Perampanel administration (Cohort 1)		A		Every day	
Electrocorticography			X		
Tumor biopsy			X		
Informed consent	X				
Demographics	X				
Medical history	X				
Concurrent Medications	X-----X				
Physical exam	X				
Vital signs	X				
Height	X				
Weight	X				
Performance status	X			Every month	
B-HCG	X ^b				
Serum chemistry ^a	X				
Seizure Frequency	X			Every month	
Tumor Measurements	X			X ^c	
Radiologic Evaluation	X			X ^c	
Adverse Event Evaluation		X-----X ^e			

A: Perampanel: Dose as assigned
 
a: Albumin, alkaline phosphatase, total bilirubin, bicarbonate, BUN, calcium, chloride, creatinine, glucose, LDH, phosphorus, potassium, total protein, SGOT [AST], SGPT [ALT], sodium.
 
b: Serum pregnancy test (women of childbearing potential).
 
c: At discretion of primary treating neuro-oncologist.
 
d: Perampanel may be continued on a clinical basis off protocol.
 
e: Adverse events will be evaluated up to 30 days after study completion.
					

11. MEASUREMENT OF EFFECT

11.1. Antitumor Effect

Although response is not the primary endpoint of this trial, participants with measurable disease will be assessed according to institutional standards at the discretion of the primary treating neuro-oncologist. For the purposes of this study, participants will be re-evaluated after every MRI for the study endpoint of progressive disease or death, defined by the criteria proposed by the Response Assessment in Neuro-Oncology (RANO) working group.³⁵

11.1.1. Definitions

Evaluable for objective response. Only those participants who have measurable disease present at baseline and have received at least one dose of therapy will be considered evaluable for response. These participants will have their response classified according to the definitions stated below. Participants who exhibit objective disease progression or die prior to the end of the first month will also be considered evaluable.

11.1.2. Disease Parameters

Measurable disease. Bidimensionally, contrast-enhancing, measurable lesions with clearly defined margins by CT or MRI scan, with a minimal diameter of 1 cm, and visible on 2 axial slices which are at least 5 mm apart with 0 mm skip. Measurement of tumor around a cyst or surgical cavity, if necessary, requires a minimum thickness of 3 mm. If there are too many measurable lesions to measure at each evaluation, the investigator must choose the largest two to be followed before a participant is entered on study. The remaining lesions will be considered non-measurable for the purpose of objective response determination. Unless progression is observed, objective response can only be determined when all measurable and non-measurable lesions are assessed.

Non-measurable evaluable disease. Unidimensionally measurable lesions, masses with margins not clearly defined, lesions with maximal diameter < 1cm.

11.1.3. Methods for Evaluation of Disease

All measurements should be taken and recorded in metric notation using a ruler, calipers, or a digital measurement tool. All baseline evaluations should be performed as closely as possible to the beginning of treatment and never more than 2 weeks before the beginning of the treatment.

The same method of assessment and the same technique should be used to characterize each identified and reported lesion at baseline and during follow-up.

11.1.4. Response Criteria

Complete response (CR). All of the following criteria must be met:

- a) Complete disappearance of all enhancing measurable and non-measurable disease sustained for at least 4 weeks. In the absence of a confirming scan 4 weeks later, this scan will be considered only stable disease.
- b) No new lesions.
- c) All measurable and non-measurable lesions must be assessed using the same techniques as baseline.
- d) Participants must be on no steroids or on physiologic replacement doses only.
- e) Stable or improved non-enhancing (T2/FLAIR) lesions.
- f) Stable or improved clinically, for clinical signs and symptoms present at baseline and recorded to be disease related. Participants with non-measurable disease cannot have a complete response. The best response possible is stable disease.

Partial response (PR). All of the following criteria must be met:

- a) Greater than or equal to 50% decrease compared to baseline in the sum of products of perpendicular diameters of all measurable enhancing lesions sustained for at least 4 weeks. In the absence of a confirming scan 4 weeks later, this scan will be considered only stable disease.
- b) No progression of non-measurable disease.
- c) No new lesions.
- d) All measurable and non-measurable lesions must be assessed using the same techniques as baseline.
- e) The steroid dose at the time of the scan evaluation should be no greater than the dose at time of baseline scan.
- f) Stable or improved non-enhancing (T2/FLAIR) lesions on same or lower dose of corticosteroids compared to baseline scan.
- g) Stable or improved, for clinical signs and symptoms present at baseline and recorded to be disease related clinically.

Participants with non-measurable disease cannot have a partial response. The best response possible is stable disease.

Progressive disease (PD). The following criterion must be met:

- a) 25% increase in sum of the products of perpendicular diameters of enhancing lesions (over best response or baseline if no decrease) on stable or increasing doses of corticosteroids

and/or one or more of the of the following:

- b) Significant increase in T2/FLAIR non-enhancing lesion on stable or increasing doses of corticosteroids steroids compared to baseline scan or best response following initiation of therapy, not due to co-morbid events (radiation therapy, demyelination, ischemic injury, infection, seizures, post-operative changes, or other treatment effects).
- c) Any new lesion.

- d) Clear clinical deterioration not attributable to other causes apart from the tumor (e.g. seizures, medication side effects, complications of therapy, cerebrovascular events, infection, etc.). The definition of clinical deterioration is left to the discretion of the investigator, but it is recommended that a decline in the Karnofsky Performance Score (KPS) from 100 or 90 to 70 or less, a decline in KPS of at least 20 from 80 or less, or a decline in KPS from any baseline to 50 or less, for at least 7 days, be considered neurologic deterioration, unless attributable to co-morbid events or changes in corticosteroid dose.
- e) Failure to return for evaluation due to death or deteriorating condition.

Stable disease (SD). All of the following criteria must be met:

- a) Does not qualify for CR, PR, or progression.
- b) All measurable and non-measurable sites must be assessed using the same techniques as baseline.
- c) Stable non-enhancing (T2/FLAIR) lesions on same or lower dose of corticosteroids compared to baseline scan. In the event that the corticosteroid dose has been increased, the last scan considered to show stable disease will be the scan obtained when the corticosteroid dose was equivalent to the baseline dose.
- d) Stable clinically. Unknown response status. Progressive disease has not been documented and one or more measurable or non-measurable lesions have not been assessed.

11.1.5. Duration of Response

Duration of overall response: The duration of overall response is measured from the time measurement criteria are met for CR or PR (whichever is first recorded) until the first date that recurrent or progressive disease is objectively documented (taking as reference for progressive disease the smallest measurements recorded since the treatment started, or death due to any cause. Participants without events reported are censored at the last disease evaluation).

Duration of overall complete response: The duration of overall CR is measured from the time measurement criteria are first met for CR until the first date that progressive disease is objectively documented, or death due to any cause. Participants without events reported are censored at the last disease evaluation.

Duration of stable disease: Stable disease is measured from the start of the treatment until the criteria for progression are met, taking as reference the smallest measurements recorded since the treatment started, including the baseline measurements.

11.1.6. Progression-Free Survival

Overall Survival: Overall Survival (OS) is defined as the time from randomization (or registration) to death due to any cause, or censored at date last known alive.

Progression-Free Survival: Progression-Free Survival (PFS) is defined as the time from randomization (or registration) to the earlier of progression or death due to any cause. Participants alive without disease progression are censored at date of last disease evaluation.

Time to Progression: Time to Progression (TTP) is defined as the time from randomization (or registration) to progression, or censored at date of last disease evaluation for those without progression reported.

11.1.7. Response Review

Review of MRI or CT scans will be performed by [name] or his designee.

11.2. **Seizure Response**

Seizure response will be evaluated every 4 weeks for the secondary endpoint of time to seizure recurrence, measured from the date of surgery. Seizure frequency will be monitored using a seizure diary form completed by participants and reviewed every 4 weeks. Baseline seizure frequency will be defined by the number of clinical seizures reported by participants in the month preceding surgery. Seizure freedom is defined by the absence of seizures.

12. DATA REPORTING / REGULATORY REQUIREMENTS

Adverse event lists, guidelines, and instructions for AE reporting can be found in Section 7.0 (Adverse Events: List and Reporting Requirements).

12.1. **Data Reporting**

12.1.1. Method

The Office of Data Quality (ODQ) will collect, manage, and perform quality checks on the data for this study.

12.1.2. Responsibility for Data Submission

Investigative sites within DF/HCC or DF/PCC are responsible for submitting data and/or data forms to the Office of Data Quality (ODQ) in accordance with DF/HCC policies.

12.2. **Data Safety Monitoring**

The DF/HCC Data and Safety Monitoring Committee (DSMC) will review and monitor toxicity and accrual data from this study. The committee is composed of medical oncologists, research nurses, pharmacists and biostatisticians with direct experience in cancer clinical research. Information that raises any questions about participant safety will be addressed with the Overall

PI and study team.

The DSMC will review each protocol up to four times a year with the frequency determined by the outcome of previous reviews. Information to be provided to the committee may include: up-to-date participant accrual; current dose level information; DLT information; all grade 2 or higher unexpected adverse events that have been reported; summary of all deaths occurring within 30 days of intervention for Phase I or II protocols; for gene therapy protocols, summary of all deaths while being treated and during active follow-up; any response information; audit results, and a summary provided by the study team. Other information (e.g. scans, laboratory values) will be provided upon request.

12.3. Collaborative Agreements Language

N/A

13. STATISTICAL CONSIDERATIONS

This is a pilot study with a primary electrophysiologic outcome and a secondary exploratory clinical outcome of seizure response. The protocol is statistically powered to detect a meaningful reduction in peritumoral hyperexcitability as measured by high frequency activity on ECoG. For the secondary outcome, this protocol is intended to estimate the seizure response effect size of early perampanel treatment on tumor-associated seizures in HGG.

13.1. Study Design/Endpoints

Pilot Study: Preliminary Study

- Primary objective: Compare rates of peritumoral HFOs (mean number of HFOs per minute) between participants treated with perampanel versus standard of care.
- Secondary objective: Compare time to seizure recurrence between participants treated with perampanel versus standard of care up to the time of HGG progression.
- Maximum total accrual: 10 participants in Cohort 1, 10 participants in Cohort 2.
- Sample size justification: Using the mean HFO rate across participants receiving standard of care (Cohort 2) as the normalized ineffective rate ($P_1=1.0$), we define a target effective rate for the treatment arm (Cohort 1) of $P_2=0.60$. Using a two sample power calculation, the intended sample size of 10 participants in each cohort will provide 82.5% power to detect a true 40% or greater reduction in the normalized mean HFO rate with perampanel compared to standard of care ($\alpha=0.05$, two-sided).
- Statistical methods for primary objective: The primary endpoint is the mean number of HFOs per minute. This will be averaged across participants in each cohort, and compared using the Mann-Whitney U test (two-sided, $\alpha=0.05$). In sensitivity analyses, we will compare HFO rates between cohorts stratified by potential confounding variables, including temporal lobe tumor location, IDH1/2 mutation, and pre-operative seizures.
- Statistical methods for secondary objective: The secondary endpoint is the time to first post-operative seizure. Time to first post-operative seizure will be estimated in time-to-event analysis from the date of surgery using the Kaplan-Meier method. Comparison

between Cohort 1 and Cohort 2 will be performed using the log-rank test ($\alpha=0.05$). In sensitivity analyses, we will compare time to first post-operative seizure between cohorts stratified by potential confounding variables, including temporal lobe tumor location, extent of resection (gross total vs subtotal resection), presence of IDH1/2 mutation, and presence of pre-operative seizures.

- Data processing and statistical analysis will be performed using R 3.5.3 (The R Foundation for Statistical Computing).
- These results will be used to support or refute the hypothesis that perampanel has targeted anti-epileptogenic activity in glioma-associated epilepsy, and may inform the design and feasibility of future clinical studies of targeting the glutamatergic pathway in this patient population.

Correlative Analysis: Intraoperative Stereotactic Molecular Imaging

- Aim 1: Correlate lactate/pyruvate ratio by mass spectrometry with HFO rate in adjacent ECoG electrodes.
- Aim 2: Correlate glutamate and GABA signal intensities by mass spectrometry imaging with HFO rate in adjacent ECoG electrodes.
- Aim 3: Correlate anti-seizure drug signal intensity by mass spectrometry imaging with HFO rate in adjacent ECoG electrodes.
- Statistical analysis: correlations will be measured using Spearman's rank correlation coefficient.

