1. OBJECTIVES

Study Hypothesis #1: Perampanel treatment reduces peritumoral hyperexcitability in newly diagnosed high grade glioma (HGG).

Study Hypothesis #2: Perampanel treatment in newly diagnosed HGG is associated with improvement in seizure control.

1 Study Design

This pilot study (Cohort 1) in participants with newly discovered radiologic lesions consistent with HGG evaluates the effect of perampanel on peritumoral hyperexcitability, measured by the rate of high frequency oscillations on intra-operative electrocorticography (ECoG), compared to a contemporary observational control group (Cohort 2) of participants undergoing ECoG and standard peri-operative seizure management. To estimate the effect size of early perampanel treatment on ongoing seizure control, participants in Cohort 1 will be maintained post-operatively on perampanel, adjusted on a clinical basis until evidence of disease progression (or maximum of 12 months), and compared to participants in Cohort 2 receiving standard of care post-operative seizure management.

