1.2 Secondary Objectives

Secondary Objective: Estimate the clinical effect of perampanel maintenance therapy on seizure control. We will measure seizure-free rates between the time of initial glioma resection and radiographic tumor progression (up to a maximum of 12 months), in participants continued on perampanel post-operatively (Cohort 1) compared to control participants (Cohort 2).

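### The seizure endpoint is meant to estimate an effect size, but Section 13.1 specifies no between-cohort effect estimate or confidence interval, only a log-rank test at 0.05

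*Combined protocol and SAP*

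**What the plan says.** Three places describe the seizure aim as estimation:

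- Section 1, Study Design, gives the reason for keeping Cohort 1 on perampanel after surgery: "To estimate the effect size of early perampanel treatment on ongoing seizure control".
- Section 1.2: "Estimate the clinical effect of perampanel maintenance therapy on seizure control". The measure named there is the seizure-free rate from resection to radiographic progression, for at most 12 months, in Cohort 1 against Cohort 2.
- Section 13, opening paragraph: "this protocol is intended to estimate the seizure response effect size of early perampanel treatment on tumor-associated seizures in HGG". The same paragraph calls this "a secondary exploratory clinical outcome of seizure response" and claims power only for the ECoG endpoint.

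Section 13.1 words the aim differently: "Compare time to seizure recurrence between participants treated with perampanel versus standard of care up to the time of HGG progression". Its methods are a Kaplan-Meier estimate of time to first post-operative seizure, counted from surgery, and a comparison "between Cohort 1 and Cohort 2 will be performed using the log-rank test" at alpha 0.05. It adds sensitivity comparisons stratified by tumour location, extent of resection, IDH status and pre-operative seizures, but gives no method or effect measure for them. Section 13.6 only refers back to 13.1.

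Section 13.1 then states: "These results will be used to support or refute the hypothesis that perampanel has targeted anti-epileptogenic activity in glioma-associated epilepsy". The sentence goes on to say that the results may also inform the design and feasibility of later studies.

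**The concern.** A log-rank test, as normally reported, gives a test statistic and a p-value. It does not say how large the difference is or how uncertain. The Kaplan-Meier curves describe each cohort separately, and the plan does not say which contrast between them will be reported, at what time, or with what interval. The effect size promised in three sections therefore has no specified form.

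Two things are at stake. Planners of a later trial need an estimate with its uncertainty, and a p-value does not supply it. With few events, a measure or time point chosen after the data are seen can also change the message. Second, a fixed 0.05 threshold, in a section that ends by saying the results will support or refute a hypothesis, leaves room for a non-significant seizure result to be read as evidence against perampanel.

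**Working it through.** The documents give no power, event count or target effect for this endpoint, so there is no figure of the plan's own to reproduce. The check asks what the planned test, and an estimate in its place, could show with this sample.

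**Inputs from the documents**
- At most 10 + 10 = 20 participants (13.1), taken as 1:1.
- Follow-up to progression, at most 12 months (1.2).
- Alpha 0.05 (13.1). Sidedness is not stated for this test; two-sided is assumed, as for the primary analysis.

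**Assumptions**
- Total first seizures D: 6 to 12, with 20 as the ceiling (every participant has one). The only related figure is in Section 2.1, seizures in up to 60% of patients with HGG, and 60% of 20 is 12. That figure is not a post-operative recurrence rate, so the range remains an assumption.
- Hazard ratio 0.5, with 0.25 and 0.3 as more extreme cases.

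**Power of the log-rank test** (Schoenfeld approximation, 1:1)

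z = |ln HR| × √D / 2; power ≈ Φ(z − 1.96)

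For HR 0.5, |ln HR| = 0.693:
- D = 6: z = 0.693 × 2.449 / 2 = 0.849; power = Φ(−1.111) = 13.3%, or 13.6% if rejections in the opposite direction are counted.
- D = 12: z = 0.693 × 3.464 / 2 = 1.200; power = Φ(−0.760) = 22.4%.
- D = 20: z = 0.693 × 4.472 / 2 = 1.550; power = Φ(−0.410) = 34.1%.

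For HR 0.25 the same formula gives about 40% with 6 events and 67% with 12. For HR 0.3 with all 20 events it gives 77%.

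**Events needed for 80% power at HR 0.5**
- Schoenfeld: 4 × (1.96 + 0.84)² / 0.693² → 66.
- Freedman: (1.96 + 0.84)² × (1.5 / 0.5)² → 71.

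Both are more than three times the maximum enrolment.

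**Check by simulation.** Simulated log-rank tests used 10 per arm, exponential times, a 12-month cap, an assumed 60% control seizure risk at 12 months and HR 0.5. Power was about 18% (9.7 events on average). With censoring at progression (assumed median 8 months) it was about 13% (6.4 events). Both agree with the approximation.

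**Precision if an estimate were reported instead.** SE(ln HR) ≈ 2/√D, so the 95% limits are the estimate divided and multiplied by exp(3.92/√D):

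| Events | Factor | 95% CI if observed HR = 0.50 |
|---|---|---|
| 6 | 4.95 | 0.10 to 2.48 |
| 8 | 4.00 | 0.13 to 2.00 |
| 10 | 3.45 | 0.14 to 1.73 |
| 12 | 3.10 | 0.16 to 1.55 |
| 20 | 2.40 | 0.21 to 1.20 |

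For a difference in seizure-free proportions with 10 per cohort, complete follow-up and 50% in each, the 95% half-width is 1.96 × √(2 × 0.25 / 10) = 0.44, or 44 percentage points. An estimate can be delivered, and its interval would show how little 20 participants can settle.

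**The case against.** The case for the plan has four parts.

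- **The material for an estimate is already there.** Kaplan-Meier gives seizure-free rates for each cohort, which is what Section 1.2 names, and their difference follows directly. The quantities behind a log-rank test can also yield a one-step (Peto) hazard ratio with an interval. This stands, and it rules out saying that the secondary objective cannot be met. The plan, however, asks for neither quantity and does not say which would be reported.
- **The log-rank test is not the only planned comparison.** Stratified comparisons are planned too. This also stands, but they name no effect measure, and they divide 20 participants further.
- **The outcome is labelled exploratory and no power is claimed.** A reader might infer from the figures above that the endpoint is wrongly underpowered. The documents do not support that: power is claimed only for the ECoG endpoint, and a 20-person pilot will be imprecise whatever method is used. The exploratory label does favour an estimate over a test against a fixed threshold.
- **The plan does not say that a non-significant log-rank test refutes anything.** The sentence about supporting or refuting follows both the primary and the secondary methods, and it also names the planning of later studies. A reader might infer a decision rule for the seizure endpoint, but none is written. What remains is that nothing in the plan prevents that reading.

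**Conclusion.** The mismatch is real, and it follows from the text alone: three sections set estimation as the aim, and the only analysis section specifies no between-cohort effect measure or confidence interval. The power and precision figures are not needed for that conclusion. They show why it matters to interpretation. If perampanel halved the hazard, the test would be non-significant about 78–86% of the time with 6–12 events, and about 66% of the time even if all 20 participants had a seizure. These figures rest on assumed event counts and hazard ratios, a two-sided test, 1:1 allocation and a large-sample approximation. They do not extend to every effect: at HR 0.25 with 12 events, a significant result would be more likely than not.

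The point should be corrected before analysis. It concerns the secondary endpoint only; the primary analysis, data collection and enrolment are unaffected.

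**What to change.** In Section 13.1:

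1. Make the secondary analysis an estimate: the hazard ratio for time to first post-operative seizure, Cohort 1 against Cohort 2, with a 95% CI. A Firth-penalised Cox model with a profile-likelihood interval is one suitable choice, because it still works if one cohort has no seizures. It is an example; other methods could serve.
2. Support it with the between-cohort difference in seizure-free probability at one prespecified time, with a 95% CI. Take it from the Kaplan-Meier curves, because follow-up ends at progression and crude proportions would mishandle participants who leave early. Keep censoring at progression as the plan has it.
3. Report the log-rank p-value as descriptive, and remove the 0.05 threshold for this endpoint.
4. State that a non-significant seizure result will not be read as refuting the hypothesis.

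The cost is a few lines of text and standard R code, using data already to be collected. The downside is that the wide interval becomes visible. The change also does not remove confounding: under Section 4, participants with a preference choose their cohort, so the estimate remains a non-randomised association and should be described as one.
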